4.1. Inclusion Criteria

Each subject must meet all the following inclusion criteria to be considered eligible for participation in this study:

1. Male and female subjects, 18 to 60 years of age inclusive, at the time of signing the informed consent
2. Subjects are in good general health as determined by the investigator or medically qualified designee, based on a medical evaluation including medical history, physical examination, laboratory tests and cardiac monitoring
3. Body weight \geq 50 kg and body mass index (BMI) within the range 18 to 32 kg/m² (inclusive)
Note: BMI = weight [kg] / (height [m])²
4. Negative serum IgG to the SARS-CoV-2
5. Negative for COVID-19 based on the nasopharyngeal or oropharyngeal swab with the method of real-time reverse transcription-polymerase chain reaction (rRT-PCR)
6. Female subjects of childbearing potential must be willing to use a highly effective method of birth control (see Appendix 5) from the time of study enrollment until 4 months after the single dose of study drug.
7. Male subjects with female partners of childbearing potential must be willing to use a highly effective method of birth control (see Appendix 5) from the time of study enrollment until 4 months after the single dose of study drug.
8. Able to provide written informed consent and can understand and agree to comply with the requirements of the study and the schedule of assessments

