4.2. Exclusion Criteria

Subjects who meet any of the following criteria will be excluded from this study:

Medical Histories or Conditions

1. History or presence of cardiovascular, respiratory, hepatic, renal, gastrointestinal, endocrinological, hematological, or neurological disorders capable of significantly altering the absorption, metabolism, or elimination of drugs, constituting a risk to the subject when taking the study drug; or interfering with the interpretation of data
2. Systolic blood pressure $>$ 150 mmHg at screening
3. Any malignancy within the past 5 years except for basal cell or squamous epithelial carcinomas of the skin that have been resected with no evidence of metastatic disease for 3 years

4. Any history of a severe allergic reaction prior to enrollment that has a reasonable risk of recurrence during the study
5. Have a medical history of SARS infection
6. Any acute fever disease or infections
7. Any chronic or clinically significant medical condition that, in the opinion of the investigator, would jeopardize the safety or rights of the subject, including but not limited to: diabetes mellitus type I, chronic hepatitis; or clinically significant forms of: drug or alcohol abuse, asthma (except for childhood asthma), autoimmune disease, psychiatric disorders, or heart disease
8. Platelet disorder or other bleeding disorder may cause injection contraindication
9. Alanine aminotransferase and/or aspartate aminotransferase $> 1.5 \times$ upper limit of normal (ULN)
10. Bilirubin $> 1.5 \times$ ULN (isolated bilirubin $> 1.5 \times$ ULN is acceptable if bilirubin is fractionated and direct bilirubin $< 35\%$)
11. Current or chronic history of liver disease or known hepatic or biliary abnormalities (with the exception of Gilbert's syndrome or asymptomatic gallstones)
12. Average Fridericia's formula (QTcF) > 450 msec (based on triplicate ECGs)
 - NOTE A: The QTc is the QT interval corrected for heart rate according to QTcF, and/or another method. It is either machine-read or manually over-read.
 - NOTE B: The specific formula used to determine eligibility or discontinuation for an individual participant should be determined prior to initiation of the study. In other words, several different formulas cannot be used to calculate the QTc for an individual participant and then the lowest QTc value used to include or discontinue the participant.

Prior/Concomitant Therapy

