7.2. Enrollment

7.2.1. Confirmation of Eligibility

The investigator will assess and confirm the eligibility of each subject. All screening results and relevant medical history must be available before eligibility can be determined. All inclusion criteria must be met and none of the exclusion criteria may apply. No eligibility waivers will be granted.

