7.3. Check-in (Day -1)

The enrolled subjects will be admitted at least 12 hours prior to the single dose of study drug. On the day of admission, the screening of alcohol/drugs and safety assessment of vital signs will be performed. Smoking will be not allowed during the inpatient stay.

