7.4. Randomization

Site personnel will access the IRT system to randomize the treatment assignment. Randomization will occur after the admission on Day -1 and before the dose of study drug on Day 1.

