8.2.3. Laboratory Safety Tests

Samples for protocol-specified clinical chemistry, hematology, urinalysis, and coagulation profiles will be evaluated by a local laboratory.

Pregnancy test will be performed for female subjects of childbearing potential during the study. Samples for pregnancy testing will also be assessed locally. The serum pregnancy test will be performed at the Screening Visit, and the next serum pregnancy test will be conducted after the admission on Day -1 and before the dose of study drug on Day 1. Female subjects of childbearing potential with negative results will be eligible to receive the study drug. Afterwards, urine pregnancy test will be performed. A serum pregnancy test must be performed if the urine pregnancy test is positive or equivocal.

See [Appendix 4](#) for the list of clinical laboratory tests to be performed and [Appendix 1](#) for the timing and frequency. Additional tests may be performed at any time during the study as deemed necessary by the investigator or as required by local regulations. If required by local regulations, clinical laboratory evaluations performed by a local (instead of a central) laboratory are acceptable.

A detailed description of the procedures for sample collection, handling, storage, and shipment of the laboratory samples and all materials such as test tubes and labels are provided in the Laboratory Manual.

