9.6.5. Pregnancies

If the partner of a male subject becomes pregnant within 30 days after the single dose of study drug, a pregnancy report form is required to be completed and expeditiously submitted to the sponsor to facilitate outcome follow-up. Information on the status of the mother and child will be forwarded to the sponsor. Generally, follow-up will be no longer than 6 to 8 weeks following the estimated delivery date. Any premature termination of the pregnancy will be reported.

While pregnancy itself is not considered to be an AE, any pregnancy complication or elective termination of a pregnancy for medical reasons will be recorded as an AE or SAE.

An abortion, whether accidental, therapeutic, or spontaneous should be always reported as a SAE. Similarly, any congenital anomaly/birth defect in a child born to a subject exposed to the study drug should be recorded and reported as a SAE.

9.6.6. Expedited Reporting to Health Authorities, Investigators, Institutional Review Boards, and Ethics Committees

The sponsor will promptly assess all SAEs against cumulative study drug experience to identify and expeditiously communicate new safety findings to regulatory authorities, investigators, IRBs, and IECs based on applicable legislation.

To determine the reporting requirements for individual SAEs, the sponsor will assess the expectedness of the SAEs using the following reference documents:

- [BGB-DXP593 Investigator's Brochure](#)

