- ^b The EOS Visit will be conducted within 7 days after a premature study discontinuation. The Day 113 Visit is the EOS Visit for subjects who complete all the previously planned study visits.
- ^c The Safety Follow-up Visit is only for subjects who discontinue the study within 30 days after the dose of study drug. The Safety Follow-up Visit will be conducted on 30 days after the dose of study drug (± 3 days). If the premature discontinuation from study occurs within 7 days prior to the timepoint of 30 days after the dose of study drug, the Safety Follow-up Visit could be combined with the EOS Visit as appropriate.
- ^d The informed consent must be obtained before performing any study-specific procedures. Consent must be obtained using the current version of the form approved by the Independent Ethics Committee/Institutional Review Board.
- ^e Follicle-stimulating hormone and estradiol assessments will be performed on female subjects who are < 55 years of age with no spontaneous menses for ≥ 12 months to identify the status of no childbearing potential. Female subjects of no childbearing potential, and female subjects of childbearing potential who are willing to use a highly effective method of birth control are eligible to participate.
- ^f Subjects will be randomized into either the active arm or control arm via IRT. Randomization will occur after the admission on Day -1 and before the dose of study drug on Day 1.
- ^g The dose will be based on the subject's actual body weight on the day of receiving the study drug (Day 1).
- ^h Height and weight will be measured at screening, and weight will be measured again before the single dose of study drug on Day 1.
- ⁱ Complete physical examination includes evaluations of 1) head, eyes, ears, nose, and throat; 2) cardiovascular; 3) dermatological; 4) musculoskeletal; 5) respiratory; 6) gastrointestinal; and 7) neurological systems. At subsequent visits (and as clinically indicated), limited, symptom-directed physical examinations will be performed.
- ^j At each timepoint, 3 consecutive 12-lead ECGs will be performed approximately 2 minutes apart to calculate heart rate and measure QT and QTcF intervals.
- ^k The cardiac telemetry will be performed from approximately 1 hour predose to 24 hours post dosing.

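### Breastfeeding is addressed nowhere in the protocol, so an otherwise eligible breastfeeding woman may be dosed with a first-in-human IgG1 whose derived half-life is about 22 days

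*Protocol*

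**What the plan says.** **Eligibility rule.** Protocol 7.2.1 makes the listed criteria decisive: "All inclusion criteria must be met and none of the exclusion criteria may apply". It allows no waivers.

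**Statements on women.** Protocol 8.2.3 requires serum pregnancy tests at screening and again between the Day -1 admission and the Day 1 dose, then says: "Female subjects of childbearing potential with negative results will be eligible to receive the study drug". Appendix 1, footnote e, accepts women of no childbearing potential and adds that "female subjects of childbearing potential who are willing to use a highly effective method of birth control are eligible to participate". Neither place mentions lactation.

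**Nearest discretionary exclusion.** Exclusion 7 in Protocol 4.2 covers "Any chronic or clinically significant medical condition that, in the opinion of the investigator, would jeopardize the safety or rights of the subject".

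**Contraception.** Inclusion 6 in Protocol 4.1 requires highly effective birth control "from the time of study enrollment until 4 months after the single dose of study drug". Enrollment has no fixed time. Section 3.1 and Section 7.2 link it to confirmed eligibility, and Section 7.3 treats subjects as already enrolled at admission: "The enrolled subjects will be admitted at least 12 hours prior to the single dose of study drug".

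**Stay in the unit.** Subjects are admitted on Day -1 and discharged on Day 8, 7 days after the dose (Sections 7.3 and 7.6.1).

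**The concern.** This is a first-in-human study with no clinical data (Section 1.2.2), and subjects receive no health benefit apart from an assessment of their medical status (Section 1.4). The toxicology summary in Section 1.2.1.2 describes a 14-day repeat-dose monkey study, tissue cross-reactivity and cytokine release. It describes no reproductive, developmental or milk-transfer study.

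The protocol does treat exposure of offspring as something to guard against. It requires contraception for 4 months after the dose and repeat pregnancy testing, and Section 9.6.5 says that "any congenital anomaly/birth defect in a child born to a subject exposed to the study drug should be recorded". A nursed infant is the one route of offspring exposure on which it is silent.

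What is at stake is participant protection. No endpoint, analysis set, sample size or escalation decision depends on this point.

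**Working it through.** **Step 1. Is there any rule on breastfeeding?** The places where one could stand, side by side:

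| Place | What it controls | Breastfeeding mentioned? |
|---|---|---|
| Protocol 4.1, inclusions 1 to 8 | Age, health, weight and BMI, SARS-CoV-2 status, contraception, consent | No |
| Protocol 4.2, exclusions 1 to 25 | History, laboratory values, prior therapy, serology, other | No; pregnancy is not listed either |
| Protocol 8.2.3 and Appendix 1, footnote p | Pregnancy test before dosing | No |
| Appendix 1, footnote e | Childbearing status and contraception | No |
| Appendix 5 | Contraception methods and definitions | No |
| Protocol 9.6.5 | Reporting of pregnancies and birth defects | No |

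Exclusion 7 does not fill the gap. It concerns a medical condition that endangers the subject. Lactation in a healthy woman is not such a condition, and her infant is not a subject. With two negative serum tests she passes the Section 8.2.3 gate. If she meets the other criteria, Section 7.2.1 gives no ground to refuse her.

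**Step 2. Reproduce Table 1.** Section 1.3.2.1 scales volumes by body-weight ratio to the power 1.0, and CL and Q to the power 0.75. The ratio is not stated, so I infer it from Vc: 2.96/0.121 = 24.46 (Vp gives 2.41/0.0984 = 24.49). Then 24.46^0.75 = 11.00, which gives:

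- CL = 0.00068 × 11.00 = 0.00748 L/h (Table 1: 0.0075)
- Q = 0.00299 × 11.00 = 0.0329 L/h (Table 1: 0.033)

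Table 1 is internally consistent.

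**Step 3. Derive the half-life.** Inputs are the human projections in Table 1: CL 0.0075 L/h, Vc 2.96 L, Q 0.033 L/h, Vp 2.41 L, in the two-compartment model that the protocol describes.

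- k10 = CL/Vc = 0.002534 per h
- k12 = Q/Vc = 0.011149 per h
- k21 = Q/Vp = 0.013693 per h
- s = k10 + k12 + k21 = 0.027375; k10 × k21 = 3.4695 × 10⁻⁵
- √(s² − 4·k10·k21) = √(7.4941 × 10⁻⁴ − 1.3878 × 10⁻⁴) = 0.024711
- β = (0.027375 − 0.024711)/2 = 0.001332 per h; α = (0.027375 + 0.024711)/2 = 0.026043 per h
- t½ = ln 2/β = 520 h = 21.7 days

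Rounding of CL and Q moves this only between 21.5 and 21.8 days. If the monkey between-animal variability in CL (26.9%) is assumed to hold in humans, one SD either way gives about 16.8 to 28.0 days.

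**Step 4. Drug left in the mother.** Treating the short infusion as a bolus, the fraction of the dose still in the body at time t is 0.951·e^(−βt) + 0.049·e^(−αt). The first weight is (k12 + k21 − β)/(α − β) = 0.02351/0.02471.

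| Visit | Days after dose | Fraction remaining |
|---|---|---|
| Day 8 (discharge) | 7 | 76% |
| Day 29 | 28 | 39% |
| Day 113 | 112 | 2.6% |

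These are maternal amounts. The documents give no input from which to compute an infant dose.

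**Step 5. When contraception begins (secondary).** Screening may run up to Day -1 (Appendix 1), and eligibility needs all screening results (Section 7.2.1). Section 7.3 calls subjects enrolled at an admission at least 12 hours before dosing. If enrollment were read as randomization, Section 7.4 puts it later still: "Randomization will occur after the admission on Day -1 and before the dose of study drug on Day 1". The protocol does not say which is meant, and no passage requires contraception during screening before enrollment.

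**The case against.** The strongest reply is that Section 8.2.3 is a laboratory rule about pregnancy tests and declares nobody eligible overall. Every other criterion still applies, and inclusion 2 leaves general health to the investigator, who may well decline a nursing mother. That is right as far as it goes. A reader might infer that the protocol positively admits breastfeeding women, and the text does not say so. It fails to exclude them, and protection then rests on unwritten discretion.

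Second, pregnancy is already controlled by two serum tests before dosing. This stands. Listing a positive test in Section 4.2 is for consistency and changes no dosing decision.

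Third, a reader might infer from the half-life that a nursed infant would be exposed for most of the 4-month contraception period. The documents do not support that: maternal half-life is not infant exposure, and milk transfer and infant absorption are not given. Mitigating facts also count. The stay from Day -1 to Day 8 covers the highest concentrations, no specific binding to normal human tissue was detected (Section 1.2.1.2), and Section 1.4 considers a pharmacodynamic effect in healthy subjects unlikely. None of these is a rule on breastfeeding, and the stay ends with most of the dose still in the body.

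Fourth, a reader might infer a defined run of days before dosing in which a conception escapes both contraception and the test. No figure in the documents fixes such a window. Several methods in Appendix 5, such as an intrauterine device or tubal occlusion, would usually predate enrollment. An earlier contraception start would also do little for women screened just before Day -1. Only the undefined time of enrollment remains.

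Finally, the Investigator's Brochure and consent form were not available and may contain advice on lactation. Neither would replace an eligibility criterion.

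**Conclusion.** The point holds in a limited form. Followed exactly, the criteria leave an otherwise eligible breastfeeding woman free to receive the study drug, and her own exposure lasts well beyond discharge: a derived terminal half-life of about 22 days, with about 76% of the dose remaining at Day 8. Those figures assume that the allometric projection in Table 1 holds in humans, and they are derived here, not stated in the plan. The size of any infant exposure is unknown from the documents. The number of women affected is also unknown, and is likely to be small in a study of up to 30 subjects.

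The change should be made because the exposure is avoidable, subjects gain no health benefit, and one line removes it. The timing of contraception is a secondary drafting point.

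**What to change.** 1. In Protocol 4.2, add breastfeeding as an exclusion criterion.
2. In the same place, list a positive pregnancy test at screening or before dosing, so that Section 4.2 agrees with the Section 8.2.3 gate.
3. Secondary: define study enrollment, and reconcile Sections 4.1, 7.2 and 7.3 on when contraception begins relative to screening and dosing. The choice of start is for the sponsor.

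**Cost.** A short amendment with no added procedure or visit. The loss of recruitment should be negligible. The SAP needs no change.

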8.2.4. Electrocardiograms

For safety monitoring purposes, the investigator must review, sign, and date all ECG tracings. Paper or electronic copies of ECG tracings (per local practice) will be kept as part of the subject's permanent study file at the site.

The subject should rest in a semirecumbent or supine position for ≥ 10 minutes in the absence of environmental distractions that may induce changes in heart rate (eg, television, radio, conversation) before each ECG collection.

At each timepoint (see [Appendix 1](#)), 3 consecutive 12-lead ECGs will be performed approximately 2 minutes apart to calculate heart rate and measure QT and QTcF intervals.

8.2.5. Cardiac Telemetry

The cardiac telemetry will be performed from approximately 1 hour predose to 24 hours post dosing. Full disclosures will be maintained as part of the subject's source documents and will be reviewed in detail.

8.2.6. Adverse Events

AEs will be graded and recorded throughout the study according to NCI-CTCAE version 5.0. Characterization of toxicities will include severity, duration, and time to onset.

All AEs, including SAEs, will be collected as described in Section [9.6](#).

8.2.7. Serology

The testing of HBV/HCV serology (hepatitis B surface antigen [HBsAg], hepatitis B core antibody [HBcAb], and HCV antibody) will be performed at screening. In the case of positive HCV antibody, the test of HCV RNA will be followed.

Blood from all subjects will be collected and tested for HIV antibody at screening. Those subjects with negative results can be enrolled.

Specific IgG antibodies against SARS-CoV-2 in the serum of all subjects will be measured by quantitative or qualitative antibody testing. Those subjects with negative results can be enrolled.

The tests mentioned above will be performed at a local laboratory.

8.2.8. Virology

The nasopharyngeal or oropharyngeal swab will be collected during the Screening and at the visit on Day 29. The nasopharyngeal or oropharyngeal swab will be tested by the method of rRT-PCR in a local laboratory for the qualitative detection of nucleic acid from SARS-CoV-2 in upper respiratory specimens. During the screening, those subjects who have negative results can be enrolled.

If any subject has positive or suspected result during the study, the subject will be discontinued from the study and treated by following local practice. If the subject is unable to complete the EOS Visit, please see the procedures in Section 7.6.2 and Section 7.6.4.

8.3. Pharmacokinetic Assessment and Antidrug Antibody Testing

Blood will be collected to characterize the PK profile of BGB-DXP593 using validated immunoassays. Blood samples will be collected for characterization of ADA. Validated screening and confirmatory assays will be employed to detect ADAs in the samples. Samples collected for analyses of blood concentration may also be used to evaluate safety or efficacy aspects related to concerns arising during or after the study.

Blood sampling for PK and ADA will be collected at the timepoints specified in the PK and immunogenicity sampling schedule ([Appendix 3](#)).

The PK and ADA assays for BGB-DXP593 will be managed through a central laboratory. Refer to the laboratory manual for instructions regarding sample collection, handling, labeling, storage, and shipping of laboratory samples. The actual time of each sample collected will be captured to the nearest minute in the eCRF and recorded in the database.

8.4. Visit Windows

The PK sampling schedule allows for a visit window of ± 1 day for the visits at Day 15, Day 22 and Day 29, and a visit window of ± 2 days for the visits at Day 43, Day 57, Day 71, Day 85, and Day 113 ([Appendix 1](#) and [Appendix 3](#)). All assessments will be performed on the day of the specified visit.

8.5. **Unscheduled Visits**

Unscheduled visits may be performed at any time at the subject's or investigator's request if there are any safety concerns. The date and reason for the unscheduled visit must be recorded in the source documentation.

If an unscheduled visit is necessary to assess toxicity, then diagnostic tests may be performed based on the investigator's assessment as appropriate, and the results of these tests should be recorded on the unscheduled visit eCRF.

9. SAFETY MONITORING AND REPORTING

The investigator is responsible for the monitoring and documentation of events that meet the criteria and definition of an AE or SAE as provided in this protocol.

9.1. Risks Associated With BGB-DXP593

This is the first-in-human study of BGB-DXP593. No clinical data are available yet and no risk associated with BGB-DXP593 has been identified. In the 14-day repeat-dose toxicology study, no apparent toxicity was observed in cynomolgus monkeys at weekly repeated doses of 30 mg/kg, 100 mg/kg, or 300 mg/kg.

